Peritoneal levels of IL-6 and TNF $\alpha$  were significantly higher in patients with colorectal anastomosis leak compared to patients without leak in some studies and may contribute to their early detection (18), having found that increased levels Serum IL-6 is a predictor of AF in gastrointestinal surgery (24).

In the retrospective study of 330 patients carried out by Yansen et al (25), the neutrophil-lymphocyte ratio (NLR) was used as a biochemical marker. The incidence of AF was 16%, 47.2% of them being treated by surgery. An increasing trend in RLN was significantly associated with the need for surgical intervention, with the mean leak diagnosis time being 7 days and 49.1% being grade III AF. An NLR cut-off value of 10 at the 3rd POD had 74.5% sensitivity, 58% specificity, 25% positive predictive value, and a value of less than 10 had 92.4% negative predictive value for leaks. The results of this study concluded that the value of NLR is more relevant in its negative predictive values and helps in making postoperative decisions with more confidence. On the contrary, an increasing trend of RLN between 1st and 3rd DPO is an independent factor of AF that should be alerted to its suspicion.

Findlay et al (26) developed a prospective study of 326 patients where it was concluded that the use of elevated inflammatory markers is more useful in diagnosis than in prediction, therefore, these parameters do not seem to be very useful for diagnosis and management. early AF. Similar conclusions were obtained in the work published by Liesenfeld et al (20) where the CRP, RGB and NU scores are not recommended as independent markers for the prediction of AF after transthoracic esophageal resection. Another retrospective study by Sugimoto et al (13) of 295 patients analyzed preparatory inflammatory and nutritional markers and studied their relationship with the appearance of postoperative AF in esophageal cancer. The study compared the predictive capacity of preoperative CAR, nutritional prognostic index (PNI), and mGPS for AF, and identified that an elevated value of preoperative CAR ( $\geq 0.0139$ ), but not PNI or mGPS, is a useful indicator for predict the occurrence of AF after esophagectomy. The results of their study suggest that preoperative CAR is a promising predictive marker of AF.

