### 4.- Sample size

The purpose of the study is to recruit as many patients as possible from all national centers who wish to participate.

For an alpha error of 5% (95% confidence) with a precision of 3% and estimating a number of patients with major complications (including AF) around 30%, the calculation of the sample size yields a total of 847 patients. However, the final sample size may be smaller depending on the proportion of complications detected and the statistical and artificial intelligence models to create the predictive model will be adapted to the event rate provided by the recruited sample.

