### 2.- Data análisis

The statistical study will be carried out with the help of the SPSS® version 23.0 software for Windows, using the MATLAB® programming environment for the preparation of the predictive model based on artificial neural networks (ANN).

In the first place, a descriptive analysis will be carried out, both of the sociodemographic and clinical variables, as well as of the analytics and the results of the study.

To describe the quantitative variables that follow a normal distribution, the mean and standard deviation will be used, and the median and interquartile range for those that do not follow a normal distribution, as well as histograms with normality curves for their graphical description.

For the qualitative variables, frequencies and percentages will be used, using bar graphs and/or sectors for the graphic description of those with greater relevance.

A univariate study will be performed to relate the variables studied with the appearance of AF and major postoperative complications. For this, different tests will be used depending on the variable to be studied:

- a) Normal categorical variables: Chi-square test or Fisher's exact test.
- b) Normal continuous variables: Student's t-test.
- c) Non-normal continuous variables: Mann-Whitney U test.

In the results obtained from the univariate study, those variables that show a  $p < 0.1$  after the application of the corresponding tests will be considered as related or candidates to predict AF or major

complications. This value will be considered more conservative, different from the conventionally accepted value of 0.05, with the intention of not ruling out potential variables that could have some influence on the results of the study.

Once the univariate study has been completed, a multivariate study will be carried out, using the logistic regression (RL) method. To do this, a recoding of the variables will be carried out, transforming the categorical variables into dummy variables. It will be verified that the variance inflation factor (VIF) is less than 2 in all cases, thus ruling out important problems of collinearity between the variables.

On the other hand, a predictive model based on artificial neural networks (ANN) will also be developed, using a Multilayer Perceptron, a multilayer neural network of forward connections, without recurrent connections and supervised learning.

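### For normal variables the plan names Student's t-test, with no unequal-variance alternative, to compare groups of clearly unequal size; naming Welch's test would be a cheap improvement

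*Combined protocol and SAP*

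**What the plan says.** Section 2 (Data analysis) of the protocol describes the univariate step as follows: "A univariate study will be performed to relate the variables studied with the appearance of AF and major postoperative complications". Test b reads "Normal continuous variables: Student's t-test" and test c reads "Non-normal continuous variables: Mann-Whitney U test". The section does not mention equal variances, a check of them, or Welch's test. A variable with p below 0.1 counts as linked to the outcome or as a candidate predictor. The threshold is looser than 0.05 on purpose, "with the intention of not ruling out potential variables that could have some influence on the results of the study". Logistic regression follows, and a multilayer perceptron is developed as well.

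On group sizes, the Sample size section says "the calculation of the sample size yields a total of 847 patients", built on about 30% major complications including leak. It allows the final number to be smaller. No leak rate is planned for this study. The Introduction cites a range of 0-34% across series, and one retrospective series in which "The incidence of AF was 16" per cent.

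**The concern.** Student's t-test pools the two variances. When the groups are of similar size, pooling does little harm even if the variances differ. When one group is much smaller, the pooled variance is dominated by the larger group. If the smaller group has the larger spread, the standard error is then too small and the p-value too small. If it has the smaller spread, both are too large.

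Unequal spread is plausible for postoperative markers. The Introduction reports a mean time to leak diagnosis of 7 days in a cited series, whereas markers are measured on days 1, 2, 3, 4 and 6. The leak group may therefore mix patients who are already unwell with patients who are not yet so.

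What is at stake is whether the p<0.1 rule really works at 10%, and so which normal variables are flagged. The same test would presumably also serve the secondary objective that compares CRP, IL-6 and procalcitonin with the occurrence of leak, for any marker treated as normal, because the section offers no other method for that comparison.

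**Working it through.** **Inputs.**
- N = 847 (Sample size section).
- Event share q = 0.16 (cited series, Introduction) or 0.30 (planned major complications, Sample size section).
- Nominal level 0.10 (Data analysis section), taken as two-sided because sidedness is not stated; z = 1.645.
- SD ratio r (event group / other group): not in the documents. Assumed values are 0.8, 1, 1.25 and 1.5.

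**The plan's own figure.** For a 30% proportion with 3% precision at 95% confidence, n = 1.96² × 0.30 × 0.70 / 0.03² ≈ 896.3, so 897 and not the stated 847. That is a separate matter. The result below depends on the share q and hardly on N, so 847 is used as stated.

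**Group sizes.** 0.16 × 847 ≈ 136, leaving 711. 0.30 × 847 ≈ 254, leaving 593. At the top of the cited leak range, 0.34 × 847 ≈ 288, leaving 559, which is still about 1:2.

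**Formula.** With the SD of the other group set to 1:
- pooled squared standard error: s²p × (1/n₁ + 1/n₂), with s²p = [(n₁−1)r² + (n₂−1)] / (N−2)
- true squared standard error: r²/n₁ + 1/n₂
- k = √(pooled / true)
- true level ≈ 2 × [1 − Φ(1.645 k)]

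In large samples k² ≈ [q r² + (1−q)] / [(1−q) r² + q]. N cancels, so a smaller final sample leaves the result nearly unchanged.

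**Example, 136 against 711, r = 1.25.**
- s²p = (135 × 1.5625 + 710) / 845 = 1.090
- pooled: 1.090 × (1/136 + 1/711) = 0.00955
- true: 1.5625/136 + 1/711 = 0.01290
- k = √(0.00955/0.01290) = 0.860, and 1.645 × 0.860 = 1.415
- true level = 15.7%

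**Results for a variable with no mean difference, nominal 10%.**

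| Groups | r = 0.8 | r = 1 | r = 1.25 | r = 1.5 |
|---|---|---|---|---|
| 136 v 711 (16%), Student | 5.6% | 10.0% | 15.7% | 20.8% |
| 254 v 593 (30%), Student | 7.2% | 10.0% | 13.2% | 15.9% |

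Simulation with normal data, 40,000 runs per cell, gives the same picture: 5.7%, 10.0%, 15.8% and 21.0% in the first row, and 7.2%, 10.1%, 13.3% and 16.1% in the second. Over all cells simulated (event shares of 5% to 34%, SD ratios of 0.5 to 2), Welch's test stayed between 9.6% and 10.3%.

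**Cost of Welch when the SDs are equal.** For a difference sized to give about 80% power at the 10% level with 136 against 711, simulated power was 79.6% for Student and 79.4% for Welch.

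**The case against.** The strongest reply has five parts.

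- **The wording is open.** The plan says Student's t-test and does not mention pooled variances. The named software, SPSS 23.0, prints an equal-variance and an unequal-variance result (general knowledge of the software, not in the documents). A reader might infer that the plan commits to the pooled test. It does so only through the usual meaning of the name. The plan still does not say which result counts, and one sentence settles that.

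- **Unequal spread is assumed.** No SD is given for any variable in either group. With equal SDs Student's test is exact however unequal the groups. This stands, and the figures above are conditional on it.

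- **A mixture also moves the mean.** Suppose half the leak group is ill and both components have SD 1. An SD ratio of 1.25 needs 1 + 0.25d² = 1.5625, so a shift of d = 1.5 and a mean difference of 0.75. The Welch statistic is 0.75/√0.01290 ≈ 6.6, and both tests select the variable. The tests part company only if few are ill: at 5%, 1 + 0.0475d² = 1.5625 gives d ≈ 3.44, a mean difference of 0.17 and a Welch statistic of about 1.5. A reader might infer that early illness in the leak group inflates false positives at the rates tabulated. That does not follow, because those rates apply only where the means are equal. A strong mixture may also be non-normal and pass to Mann-Whitney. This stands: the mixture argument makes unequal spread plausible but does not supply the size of the error.

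- **It is only a screen.** The threshold is deliberately loose, so extra false candidates are a cost the plan accepts. This largely stands. The reverse case (event-group SD smaller) would make the rule stricter than intended, against the plan's stated aim, but the documents give no reason to expect that pattern. A reader might infer that the final models are damaged. The documents do not show this, and they do not say that the neural network uses only screened variables.

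- **Confidence intervals.** A reader might extend the argument to intervals for mean differences. The section plans none, so no claim is made about them.

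**Conclusion.** The point holds as a minor improvement to the specification. The event group is the smaller one at every rate the documents cite, and the named test, in its usual sense, relies on equal variances that the plan neither asserts nor checks. The departures from 10% in the table rest on the assumed SD ratios. The 16% share comes from one cited retrospective series and is not a planning value for this study. At the planned 30% complication rate the departures are milder.

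The consequence is confined to which normally distributed variables are flagged as related or as candidates, and to reported marker comparisons made with this test. It does not follow that the planned p-values are wrong: that depends on spreads that nobody knows yet.

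**What to change.** In test b of the Data analysis section, replace the entry by: 'Normal continuous variables: Welch's t-test (unequal variances), for all such variables'. Do not make the choice depend on a preliminary test of equal variances, since that adds a data-driven step and is unnecessary when Welch performs well in both situations.

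The cost is a change to one line. It needs no further patients, visits or data. The only statistical downside is a negligible loss of power when the variances are in fact equal, about 0.2 percentage points in the case simulated (79.6% − 79.4%).

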## OBJECTIVES

Based on the hypothesis of the study, the main and secondary objectives of this study are established:

- Main goal:

\*Design a predictive model based on clinical and analytical variables that allow identifying patients with a high risk of anastomotic leak (main variable) during the postoperative period of esophagogastric surgery.

- Secondary objectives:

\* Design a predictive model based on clinical and analytical variables that allow identifying patients at high risk of other major complications (Clavien-Dindo greater than 3) during the postoperative period of esophagogastric surgery.

\* Individually describe the postoperative evolution of the clinical and analytical parameters studied in patients without major complications or AF and those who did suffer from any of them.

\* Describe the complications and types of AF diagnosed in the study.

\* Assess the day AF was diagnosed and the treatment used for its possible resolution.

\* Assess the day AF was diagnosed and hospital stay.

\* Compare the preoperative Glasgow prognostic score (mGPS) and the biochemical value of inflammatory markers (CRP, Interleukin 6 (IL-6) and procalcitonin) and the appearance of AF.

\* Assess the AF resolution capacity of each technique used.

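### The univariate p<0.1 threshold is a permissive screen, but the plan calls it more conservative than 0.05 and also lets it label a variable as related to leak

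*Combined protocol and SAP*

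**What the plan says.** Under DATA COLLECTION AND ANALYSIS, 2.- Data análisis, the plan sets out a univariate step: "A univariate study will be performed to relate the variables studied with the appearance of AF and major postoperative complications". AF here means anastomotic leak. The tests are chi-square or Fisher's exact, Student's t and Mann-Whitney.

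The rule applies to "those variables that show a $p < 0.1$ after the application of the corresponding tests". These "will be considered as related or candidates to predict AF or major" complications. The threshold is then described: "This value will be considered more conservative, different from the conventionally accepted value of 0.05", and the same sentence gives its purpose: "with the intention of not ruling out potential variables that could have some influence on the results of the study". After that, "a multivariate study will be carried out, using the logistic regression (RL) method", and a neural network is also built. No significance level or retention rule is stated for the regression.

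OBJECTIVES lists a separate secondary aim: "Compare the preoperative Glasgow prognostic score (mGPS) and the biochemical value of inflammatory markers (CRP, Interleukin 6 (IL-6) and procalcitonin) and the appearance of AF". The analysis section gives this aim no test, time point or threshold of its own.

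The only other alpha is in 4.- Sample size: "For an alpha error of 5% (95% confidence) with a precision of 3"%. There it is the confidence level for estimating a proportion, not a rule for hypothesis tests.

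**The concern.** One threshold is given two jobs. Nominating variables for a multivariable model is screening, and a loose cut-off can be defended for that. Calling a variable related to leak is a statement of association, and a loose cut-off weakens it. The description of the threshold makes this worse, because in terms of false positives it has the direction reversed.

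An analyst following the text could report a marker with p = 0.08 as related to leak and cite a threshold labelled conservative. The Introduction describes the evidence on these markers as limited, and the studies it reviews disagree. Poorly controlled statements of association would add to the uncertainty the study is meant to reduce.

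**Working it through.** The plan states no false-positive rate for these tests, so there is no figure of its own to reproduce on this point. The 847 patients in 4.- Sample size come from a precision calculation and are not used here.

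**Inputs from the documents**
- Threshold: p<0.1 (2.- Data análisis). Sidedness is not stated; two-sided is assumed.
- Comparator: 0.05, named in the same paragraph as the conventional value.
- Markers in the secondary objective: four (mGPS, CRP, IL-6, procalcitonin).
- Measurement times: preoperative and days 1, 2, 3, 4 and 6, so six (8.2.2).

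**Assumptions, not in the documents**
- Each of the four markers is tested once against leak.
- None is truly related to leak.
- The test statistics share a common correlation ρ, varied from 0 to 0.8.

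**Step 1: direction of the threshold.** The per-test false-positive rate is the threshold itself: 0.10 / 0.05 = 2. The rule allows twice as many false positives per test as 0.05, so it is the more permissive of the two.

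**Step 2: four independent tests.** The chance of at least one false positive is 1 − (1 − α)^4.
- α = 0.10: 1 − 0.9^4 = 1 − 0.6561 = 0.344
- α = 0.05: 1 − 0.95^4 = 0.185
- α = 0.0125 (0.05/4): 1 − 0.9875^4 = 0.049

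**Step 3: four correlated tests.** Take Z_j = √ρ·C + √(1 − ρ)·E_j for j = 1 to 4, with C and E_j independent standard normal. Count how often the largest |Z_j| exceeds the two-sided critical value. Simulation with 500,000 draws and numerical integration agree to the nearest percent for α = 0.10 and 0.05.

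| α per test | ρ = 0 | ρ = 0.3 | ρ = 0.5 | ρ = 0.8 |
|---|---|---|---|---|
| 0.10 | 34% | 32% | 29% | 21% |
| 0.05 | 19% | 17% | 16% | 11% |
| 0.0125 | 4.9% | 4.7% | 4.3% | 3.2% |

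Moving from 0.10 to 0.05 roughly halves the rate. What remains at 0.05 comes from testing four markers without adjustment.

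**Step 4: if the objective covers more than one day.** In the objective, *preoperative* stands next to mGPS, and no time is given for the biochemical markers. If the three biochemical markers were each tested at all six times, plus mGPS once, there would be 3 × 6 + 1 = 19 tests. The independent figure would be 1 − 0.9^19 = 0.86. Repeated measurements on the same patient are likely to be correlated, which would lower it.

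**The case against.** The strongest reply is that p<0.1 is only a pre-selection filter. The purpose clause says so, logistic regression follows directly, and *conservative* can be read as cautious about discarding variables. Most of this stands: as a screen, the threshold is not challenged here. It does not cover the word *related*, which the plan offers alongside *candidates*, and nothing states that passing the screen is not evidence of association.

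A reader might infer that the plan decides the secondary marker objective at 10% per test. It does not say that. The link holds only by default, because no other rule is given. The plan names 0.05 as conventional, and the logistic regression could also estimate these associations, though without a stated level.

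A reader might also take one false-positive figure, such as 29%, as a property of the plan. It is not: it needs exactly four tests, no true associations and a correlation of 0.5, and the documents give no correlation. Nor should these family-wise rates be set against the 5% in 4.- Sample size as if that were a promised error rate, since that 5% belongs to a precision calculation.

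Finally, a formal multiplicity adjustment may be too much for a secondary objective of an observational model-development study. That is fair. By normal approximation, a test with 80% power at two-sided 0.10 has a mean statistic of 1.645 + 0.842 = 2.487. Against the first Holm critical value of 2.498 (0.05/4 = 0.0125), power is Φ(2.487 − 2.498), about 50%. Adjustment should be optional.

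**Conclusion.** The plan is wrong as written on two narrow matters: it describes 0.1 as more conservative than 0.05, and it allows p<0.1 to label a variable as related to an outcome. Both follow from the text and need no assumption. The per-test false-positive rate is twice that at 0.05.

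The consequence for the secondary marker objective is a default reading. Its size is illustrative: 34% for four independent tests with no true associations, about 21% to 32% at assumed correlations of 0.8 to 0.3, and a different figure if the biochemical markers are tested on several days.

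Severity is minor. The primary objective is a prediction model, and this point does not affect it.

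**What to change.** In 2.- Data análisis:

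1. Describe the threshold as more permissive than 0.05.
2. Delete *related or* from the rule, and state that p<0.1 only nominates candidates for the model and is not evidence of association.
3. Report the marker comparisons in the secondary objective, and all other univariate results, as exploratory, with effect estimates and 95% confidence intervals.
4. If the sponsor wants a formal claim for the four markers, state which time point is tested and use 5% with a multiplicity adjustment such as Holm.

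The cost is a few sentences, with no new data or patients. The downside is that fewer variables can be described as related to leak. Option 4 also carries the loss of power shown above.

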In addition, once the model has been designed, an application for mobile devices and/or a web page will be created to prospectively introduce new data on developing cases, in order to obtain predictive information on the possibility of developing AF or a major postoperative complication in each case. in particular, thus being able to help the clinician in decision-making during the postoperative control of these patients.

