### **5.-Schedule:**

The schedule of the study is presented schematically below:

5.1.- Conceptual or theoretical phase: choice of topic, literature review, goal setting, hypothesis development: 1 month (November 2021).

5.2.- Design phase: choice of design and choice of variables, development of database and schedule: 1 month (December 2021).

5.3.- Evaluation, approval and authorization of the study by the Research and Ethics Committee of one of the collaborating centers (January 2022).

5.4.- Dissemination and adhesion phase: presentation and dissemination of the project to the Spanish Association of Surgeons, the Esophagogastric Surgery Section and all the centers that wish to collaborate in it (January 2022). The centers may gradually join the study until June 2022.

5.5.- Empirical phase: recruitment and collection of patient data, surgical intervention, results and follow-up. In each center, the data of consecutively operated patients during the period of 1 year from the inclusion of the first case will be collected. Access to the medical records of participating patients will only be allowed to researchers at each center. The data will be collected in each of the participating hospitals and the custody of the same will be the responsibility of the main coordinator or person in charge in each center, who will be in charge of guaranteeing that no identifying data of the patients is transmitted. The data will be encrypted by generating a unique code that will be the only one that will be sent to the central coordination team.

5.6.- Interpretive phase: once the recruitment period for all the centers has closed, the data will be analyzed, the results discussed and compared with other studies. The predictive model described and reason for the study will be created. The estimated duration of this phase will be 3 months.

5.7.- Communicative phase or dissemination of results. Communication of the results to all the participating centers and writing and preparation of scientific articles and communications to congresses (national and international scope). All those responsible for each center will appear as co-authors in all the works and communications published, establishing the order of appearance in them based on the number of cases included in the study. The estimated time for the preparation of this material will be approximately 1 month.

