5.8.- Creation and dissemination of the predictive tool. Creation of an application for mobile devices and/or web page where the data of new cases can be entered prospectively, obtaining the prediction of a possible AF or major postoperative complication in each new patient. The estimated time for the creation of this tool will be approximately 3-4 months. Once it has been created and its correct functioning has been tested, it will be disseminated. With the new data entered, an evaluation of the effectiveness and profitability of the model will be carried out, which will supposedly improve with the introduction of more data.

5.9.- Development of sub-studies: once the previous stages have been completed, different sub-studies proposed by the project collaborators will be developed. The collaborator or collaborators who have

proposed the sub-study will be the coordinator and responsible for it, appearing as the first or first signatories in the communications and publications that arise from its realization.

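### No internal validation, performance measure or model-choice rule is planned for the prediction models, and effectiveness is evaluated only after the app is released

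*Combined protocol and SAP*

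**What the plan says.** The modelling plan is in DATA COLLECTION AND ANALYSIS, 2.- Data análisis. Each variable is tested against the outcome, and those with p<0.1 "after the application of the corresponding tests will be considered as related or candidates to predict AF or major" complications. Then: "Once the univariate study has been completed, a multivariate study will be carried out, using the logistic regression (RL) method". Categorical variables become dummies, and VIF is to be checked as below 2. Separately, "a predictive model based on artificial neural networks (ANN) will also be developed, using a Multilayer Perceptron"; only the type of network is given. The section ends with a mobile or web app, "thus being able to help the clinician in decision-making during the postoperative control of these patients".

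Under 5.-Schedule, item 5.6 says that "the data will be analyzed, the results discussed and compared with other studies" and that the model will be created. Item 5.8 covers the app: "Once it has been created and its correct functioning has been tested, it will be disseminated". The next step is: "With the new data entered, an evaluation of the effectiveness and profitability of the model will be carried out".

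**The concern.** The model is the main objective, and its output is meant to inform care of individual patients. The same patients are used to pick predictors and to estimate coefficients, so any accuracy figure computed on them is biased upward. The screen adds to this, because about one unrelated candidate in ten passes p<0.1 by chance.

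The only two numerical rules, p<0.1 and VIF<2, concern screening and collinearity. Neither measures how well the model predicts. Two models will exist, with no stated basis for preferring one. In the order given in 5.8, clinicians can be using the app before the plan requires any accuracy result free of this bias.

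**Working it through.** **1. The plan's own figure.** The only sample-size figure is 847, for estimating a 30% proportion to within 3 points. The usual formula gives z²p(1-p)/d² = 1.96² × 0.30 × 0.70 / 0.03² = 896.4, so 897; 847 is not reproduced. That is a separate matter. I use 847 below only because it is the stated target.

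**2. Text check.** I looked for any planned split, cross-validation, bootstrap, AUC, calibration measure, accuracy target or model-choice rule.
- Data analysis section: none.
- 4.- Sample size: the models will be adapted to the event rate; no method or measure.
- Distribution of tasks, 4.3: modelling is assigned to a university data-analysis laboratory; no validation task.
- Schedule 5.6: comparison with other studies; no measure to compare.
- Schedule 5.8: a functioning test with no data set, metric or threshold, and effectiveness as a later step.

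Sensitivity, specificity and predictive values appear only for cited studies in the Introduction. Validation appears only in reference titles.

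**3. Number of candidates, before dummy coding.** General data (8.2.1), without free text and date: 35. Serial variables (8.2.2): 20, at six time points.
- One day: 35 + 20 = 55
- One day plus preoperative: 35 + 2 × 20 = 75
- All time points in one screen: 35 + 6 × 20 = 155

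With three true markers, the unrelated candidates number 55 - 3 = 52, 75 - 6 = 69 and 155 - 18 = 137. At p<0.1 about 5, 7 and 14 of these are expected to pass.

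**4. Illustrative simulation of the logistic model.** Assumptions: n = 847; three true markers with odds ratio (OR) 1.5 or 2 per SD; correlation 0.6 between time points of a marker; t-test screen at p<0.1; all screened variables entered; the variable with the largest VIF dropped until all are below 2. Event rates: 10% (assumed), 16% (leak rate of a cohort cited in the Introduction) and 30% (the sample-size figure for major complications including leak). There were 200 cohorts per scenario, each tested on 5,000 new patients. Optimism = apparent AUC - new-patient AUC.

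| Candidates | OR | Apparent AUC at 10/16/30% | New patients | Optimism |
|---|---|---|---|---|
| 55 | 1.5 | 0.737/0.720/0.709 | 0.640/0.653/0.660 | 0.097/0.067/0.049 |
| 55 | 2 | 0.813/0.802/0.789 | 0.760/0.761/0.760 | 0.053/0.041/0.029 |
| 75 | 1.5 | 0.751/0.730/0.714 | 0.633/0.643/0.654 | 0.118/0.087/0.060 |
| 75 | 2 | 0.822/0.808/0.794 | 0.751/0.755/0.756 | 0.071/0.053/0.038 |
| 155 | 1.5 | 0.768/0.742/0.717 | 0.607/0.615/0.622 | 0.161/0.127/0.095 |
| 155 | 2 | 0.825/0.801/0.776 | 0.698/0.708/0.708 | 0.127/0.093/0.068 |

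The calibration slope in new patients (1 is ideal; below 1 means predicted risks too extreme) was 0.57-0.88 with 55 candidates, 0.50-0.84 with 75 and 0.36-0.70 with 155. The sample-size section allows a smaller sample; at an assumed n = 500, optimism was 0.05-0.17 with 55-75 candidates.

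**5. Which validation removes the bias** (n = 847, 100 cohorts per scenario).
- 10-fold cross-validation repeating the screen and VIF removal: within -0.013 to +0.001 of the new-patient AUC.
- 70/30 hold-out with screening inside the training part: -0.014 to +0.006.
- 70/30 hold-out made after screening on all patients: still 0.02-0.07 too high with 55-75 candidates.
- Cross-validation of the final fit only: also 0.02-0.07 too high with 55-75 candidates.

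**The case against.** **Validation may be intended.** A specialist laboratory builds the models and may well validate them without the protocol saying so. The plan does not exclude a hold-out, and 5.7 places communication of results before the app phase. This softens the point, since some reporting will probably precede release. It does not answer it: none of these items names a validation method or a measure, and step 5 shows that a hold-out helps fully only if the screen is repeated inside the training part.

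**The functioning test may include accuracy.** It could, but the sentence is about the tool, sets no standard, and lists effectiveness separately afterwards.

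**The simulation assumes steps the plan does not state.** This is correct. The plan calls the screened variables candidates and does not say that all enter the model. It says VIF will be verified, not that variables will be dropped. No section asks for all 155 terms in one screen. All three counts also include pathological T, N and M, which come from the resected specimen. The 55-75 results are therefore the ones to read, and only as an indication of size.

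**A stronger inference does not hold.** A reader might infer that the model would do worse than one good marker, such as the neutrophil-lymphocyte ratio cited in the Introduction. A simulation in which one marker carries all the signal does show this, but by construction: that marker alone is then the true model. In a repeat of the three-marker scenarios (80 cohorts per cell), the model's mean new-patient AUC was at least that of one true marker in all 18 cells; for OR 2 and 55 candidates it was 0.76 against 0.66-0.67. The Introduction also reports a combined score outperforming its single components.

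**Conclusion.** The point stands as a cheap improvement. No internal validation, performance measure or model-choice rule is planned for either model, and 5.8 places the evaluation of effectiveness after dissemination. This rests on the text alone.

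The size depends on the assumptions in step 4. If performance is taken from the development patients, the logistic AUC is about 0.03-0.12 too high with 55-75 candidates, with a calibration slope of about 0.50-0.88. In the less likely case of one screen over all 155 terms, the excess reaches about 0.16. The documents give no expected leak rate, final predictor list or signal strength, so these are illustrations and not forecasts. No figure is given for the perceptron, because its inputs, size and training rule are not stated. The documents do not show that the sponsor will rely on apparent performance, nor that the model would be inferior to a single marker.

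**What to change.** **Data analysis section.** Add bootstrap or cross-validation that repeats every data-driven step inside each resample: the p<0.1 screen, any variable removal made to meet VIF<2, and the network's input choice and tuning. Report optimism-corrected AUC and calibration slope and intercept for both models, and state that these results decide which model goes into the app.

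**Schedule 5.8.** Before dissemination, and in addition to the functioning test, require the corrected performance to be reported and judged against a criterion that the sponsor sets before the analysis.

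**Optional.** A comparison with the NUn score in the patients to whom it applies, since its day 4 inputs are already collected. A by-centre check such as leave-one-centre-out, if centre sizes allow, given the aim of equal effectiveness across centres in LIMITATIONS OF THE STUDY, item 4.

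**Cost.** Two additions to the text and computing time; no extra patients or measurements. The headline AUC will be lower and release may be later. Some scripting is needed: "The statistical study will be carried out with the help of the SPSS® version 23.0 software for Windows", with MATLAB named only for the network, so the screen and VIF steps must be coded before they can be resampled.
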